4.5 Adverse Event Reporting

Detailed information concerning adverse events will be collected and evaluated throughout the conduct of the protocol.

The NICHD Program Scientist and the BCC will be notified within seventy-two hours of any maternal or neonatal death by email/phone/fax, if the event occurred in a MFMU Network hospital. For any maternal or neonatal death occurring outside a MFMU Network hospital, the adverse event must be reported to the NICHD and the BCC within twenty-four hours of being notified. These and other adverse events deemed serious, unexpected and definitely, possibly or probably related, will be immediately (within twenty-four hours of notification) forwarded by the BCC to the DSMC Chair, NIH representative, and any other DSMC member who requests notification. If a death is reported, a copy of the patient's medical record will be made.

Adverse events which do not qualify under the above definition must be reported to the BCC within 7 days of being notified. These adverse events will be collected and sent to the Chair, NIH representative, and any other requesting DSMC member on a monthly basis. The Chair decides whether the adverse event reports should be disseminated to the rest of the committee and whether a follow-up call or meeting is required. NICHD representatives may also request follow-up of specific events. All adverse events will be considered along with other interim safety data in the DSMC deliberations.

An IDE safety report will be completed for any suspected adverse reaction to the pessary that is both serious and unexpected.

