4.6 Study Outcome Measures and Ascertainment

4.6.1 Primary outcome

The primary outcome is delivery or fetal demise prior to 37 weeks 0 days (as determined by the project gestational age).

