4.6.3 Fetal and Neonatal Secondary outcomes

1. Fetal or neonatal death
2. Duration of ventilator support
3. Duration of supplemental oxygen
4. Seizures requiring treatment
5. Small for gestational age defined as < 5th percentile weight for gestational age, assessed specifically by sex and race of the infant based on United States birth certificate data
6. Intraventricular hemorrhage (IVH) grades III or IV as determined by cranial ultrasounds performed as part of routine clinical care and classified based on the Papile classification system
7. Retinopathy of prematurity (ROP). This diagnosis will be reached when an ophthalmologic examination of the retina has been performed and ROP is diagnosed at Stage I (demarcation line in the retina) or greater.
8. Respiratory distress syndrome (RDS) defined as the presence of clinical signs of respiratory distress (tachypnea, retractions, flaring, grunting, or cyanosis), with an oxygen requirement and a chest x-ray that shows hypoaeration and reticulogranular infiltrates.
9. Bronchopulmonary dysplasia (BPD) defined as oxygen requirement at 28 days of life or at 36 weeks project gestational age for infants born before 32 weeks.
10. Necrotizing Enterocolitis (NEC), defined as modified Bell Stage 2 or 3 where stage 2 represents clinical signs and symptoms with pneumatosis intestinalis on radiographs and stage 3 is defined as advanced clinical signs and symptoms, pneumatosis, impending or proven intestinal perforation.
11. Hyperbilirubinemia. Peak total bilirubin of at least 15 mg% or the use of phototherapy
12. Neonatal infectious morbidity
 - Sepsis (within 72 hours and > 72 hours after birth). The diagnosis of sepsis will require the presence of a clinically ill infant in whom systemic infection is suspected with a positive blood, CSF, or catheterized/suprapubic urine culture; or, in the absence of positive cultures, clinical evidence of cardiovascular collapse or an unequivocal radiograph confirming infection.
 - Suspected sepsis. The diagnosis of suspected sepsis will include infants with suspicious clinical findings of infection, but no positive cultures or radiographs.
 - Pneumonia. The diagnosis of pneumonia will be confirmed by radiograph or positive blood culture.

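### Section 4.5 expedites every maternal or neonatal death whatever its cause, but a fetal death only if it is judged serious, unexpected and at least possibly related

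*Combined protocol and SAP*

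**What the plan says.** Section 4.5 sets out three routes to the DSMC Chair.

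- **Deaths, automatic.** For events in a Network hospital, the NICHD Program Scientist and the BCC "will be notified within seventy-two hours of any maternal or neonatal death by email/phone/fax". The companion sentence begins "For any maternal or neonatal death occurring outside a MFMU Network hospital" and sets a limit of 24 hours from being notified. Both sentences name maternal and neonatal death only, and neither asks about cause.
- **Other events, by judgement.** "These and other adverse events deemed serious, unexpected and definitely, possibly or probably related, will be immediately (within twenty-four hours of notification) forwarded"; the Chair is among the recipients. This route is open to any type of event, fetal death included, if all the conditions are met.
- **Everything else.** "Adverse events which do not qualify under the above definition must be reported to the BCC within 7 days of being notified". These are then "sent to the Chair, NIH representative, and any other requesting DSMC member on a monthly basis".

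Section 4.5 also requires an IDE safety report for a suspected reaction to the pessary that is both serious and unexpected.

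On the endpoint side, Section 4.6.1 reads "The primary outcome is delivery or fetal demise prior to 37 weeks 0 days". The first item of Section 4.6.3 is "Fetal or neonatal death", and the same pair is one component of the neonatal composite in item 13.

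**The concern.** The outcome definitions group fetal and neonatal death together. The reporting rule separates them and gives no reason. Two pregnancies lost at the same early gestation can therefore take different routes, depending only on whether death came before or after birth.

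The distinction matters in this trial. Women are randomized from 16 weeks 0 days (Section 3.4.1), when a loss may well be fetal. The protocol itself sees a possible harm pathway: several exclusions in Section 3.4.4 are justified by the chance that the pessary could worsen bleeding or infection, including ascending infection after membrane rupture.

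The formal stopping boundaries in Section 5.4 apply to the primary outcome, which counts a loss at 20 weeks and a live birth at 36 weeks alike. If a pregnancy that would have ended in a live preterm birth ends in fetal death instead, that count does not move. Prompt notice of individual deaths is one of the faster signals available to the DSMC Chair, and as written it is automatic for some deaths and discretionary for others.

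**Working it through.** The plan states no overall time from event to DSMC Chair, so there is no figure to reproduce. The check follows each route in Section 4.5 and adds its stated limits.

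**Inputs (all Section 4.5).** Site to BCC: 72 hours for a death in a Network hospital, 24 hours from being notified for a death elsewhere, 7 days from being notified for the residual class. BCC to Chair: 24 hours for expedited events, monthly for the residual class. Assumption: one monthly cycle is at most 31 days.

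**Longest time to the Chair = site limit + BCC limit**

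| Event | Sum | Result |
|---|---|---|
| Maternal or neonatal death, Network hospital | 72 h + 24 h = 96 h | 4 days |
| Maternal or neonatal death, elsewhere | 24 h + 24 h = 48 h | 2 days after the site is notified |
| Fetal death judged serious, unexpected and at least possibly related | 24 h | 1 day after notification |
| Fetal death not so judged | 7 d + up to 31 d | up to 38 days (38/7 = 5.4 weeks) |

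The largest gap is 38 − 4 = 34 days against a neonatal death in a Network hospital, or 38 − 2 = 36 days against one elsewhere. If the monthly batch happens to leave on the day the BCC receives the report, the last row falls to 7 days. Two cautions apply. The clocks do not all start at the same moment: the 72 hours appear to run from the death, the 24 hours and 7 days from the site's being notified. The 1 day in the third row is the BCC's forwarding limit; Section 4.5 gives no separate site-to-BCC limit for that class.

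**What decides between the last two rows.** All three conditions must hold. Section 4.5 defines neither seriousness nor expectedness and does not say who judges them. The trial is unblinded (Section 3.3), so relatedness is judged with the arm known. Fetal demise is a primary-outcome event in a high-risk population, so nothing in the text stops a site from calling it expected. Section 4.5 also does not say whether a fetal demise already counted as an outcome must be reported as an adverse event at all.

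**Other safeguards.** The IDE report applies the same filter for expectedness, plus suspicion of the pessary. DSMC reports include all outcome variables (Section 6.4), but meetings are guaranteed only once a year and one interim analysis is expected, at about 50% of 850 = 425 women (Section 5.4). For the monthly reports, the Chair decides whether the rest of the committee sees them (Section 4.5).

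**The case against.** A reader might infer that a fetal loss caused by the pessary can reach the DSMC only in the monthly batch, or that every fetal death in the trial is delayed. The documents do not support either reading. The second route in Section 4.5 sends a serious, unexpected and even possibly related event to the Chair within 24 hours of notification, and a loss thought to be due to the device is the kind of event that can qualify. The pessary trials summarized in Section 2.6 reported no serious adverse effects of the device in one case, and no difference in ruptured membranes or adverse neonatal outcomes in another. On that record, a site could well call a device-attributed fetal death unexpected.

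Nor do the documents support saying that sites will usually call such losses expected, or that a large share of deaths is left out. They hold no list of expected events and no count of fetal deaths.

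It can also be said that fetal death is tabulated in the DSMC reports, that an excess between arms is found in tables rather than in single reports, that the DSMC may act on safety grounds outside the boundaries (Sections 5.4 and 7.2.4), and that the manual of operations mentioned in Section 1.3 may add detail. At about 34 enrollments a month (Section 8.2), a monthly batch is not obviously slow.

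Much of this stands and limits the size of the point. It does not explain why a neonatal death, also foreseeable in this population, is expedited without any judgement while a fetal death is not.

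**Conclusion.** The gap is real but limited. The cause-independent rule leaves out fetal death, so its prompt reporting depends on a judgement that Section 4.5 neither defines nor assigns. For a fetal death that fails any of the three conditions, the stated limits allow up to about 38 days to the DSMC Chair, against 2 to 4 days for a neonatal death. This assumes that the event is reported as an adverse event, that the site uses its full 7 days, and that the report waits a whole monthly cycle. The number of fetal deaths affected is not known from the documents. The point concerns speed and consistency of safety reporting; it does not touch sample size, power, alpha or the primary analysis. It is a cheap improvement worth making, not a flaw that threatens the trial's conclusions.

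**What to change.** In both sentences of Section 4.5, add fetal death, so that the rule covers *any maternal, fetal or neonatal death after randomization*. Fetal deaths would then follow the same 72-hour or 24-hour route and go to the DSMC Chair whatever their judged relatedness or expectedness. This also settles that a fetal demise counted as an outcome must still be reported.

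The cost is a short wording change in a protocol amendment and some extra expedited paperwork for sites and the BCC, for losses that are foreseeable here. No visits, procedures or patients are added.

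The change should stop at single-event reporting. A running count of deaths by arm would give repeated looks at a component of the primary outcome outside the interim analysis in Section 5.4. Comparison by arm should stay in the DSMC reports.

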4.6 Study Outcome Measures and Ascertainment

4.6.1 Primary outcome

The primary outcome is delivery or fetal demise prior to 37 weeks 0 days (as determined by the project gestational age).

4.6.2 Maternal Secondary Outcomes

1. Interval from randomization to delivery or fetal demise
2. Gestational age at delivery
3. Preterm delivery or fetal demise prior to 28 weeks, 32 weeks or 35 weeks
4. Preterm premature rupture of membranes (pPROM)
5. Spontaneous preterm delivery (following preterm labor or pPROM)
6. Indicated preterm delivery

7. Cesarean delivery
8. Chorioamnionitis
9. Maternal antepartum hospitalization days
10. Maternal antibiotic or antifungal use for vaginal infection
11. Vaginal infection as assessed by local clinical diagnosis
12. Treatment for preterm labor, including cervical cerclage
13. Side effects including symptomatic vaginal discharge or discomfort
14. Discontinuation of pessary treatment and reason

4.6.3 Fetal and Neonatal Secondary outcomes

1. Fetal or neonatal death
2. Duration of ventilator support
3. Duration of supplemental oxygen
4. Seizures requiring treatment
5. Small for gestational age defined as < 5th percentile weight for gestational age, assessed specifically by sex and race of the infant based on United States birth certificate data
6. Intraventricular hemorrhage (IVH) grades III or IV as determined by cranial ultrasounds performed as part of routine clinical care and classified based on the Papile classification system
7. Retinopathy of prematurity (ROP). This diagnosis will be reached when an ophthalmologic examination of the retina has been performed and ROP is diagnosed at Stage I (demarcation line in the retina) or greater.
8. Respiratory distress syndrome (RDS) defined as the presence of clinical signs of respiratory distress (tachypnea, retractions, flaring, grunting, or cyanosis), with an oxygen requirement and a chest x-ray that shows hypoaeration and reticulogranular infiltrates.
9. Bronchopulmonary dysplasia (BPD) defined as oxygen requirement at 28 days of life or at 36 weeks project gestational age for infants born before 32 weeks.
10. Necrotizing Enterocolitis (NEC), defined as modified Bell Stage 2 or 3 where stage 2 represents clinical signs and symptoms with pneumatosis intestinalis on radiographs and stage 3 is defined as advanced clinical signs and symptoms, pneumatosis, impending or proven intestinal perforation.
11. Hyperbilirubinemia. Peak total bilirubin of at least 15 mg% or the use of phototherapy
12. Neonatal infectious morbidity
 - Sepsis (within 72 hours and > 72 hours after birth). The diagnosis of sepsis will require the presence of a clinically ill infant in whom systemic infection is suspected with a positive blood, CSF, or catheterized/suprapubic urine culture; or, in the absence of positive cultures, clinical evidence of cardiovascular collapse or an unequivocal radiograph confirming infection.
 - Suspected sepsis. The diagnosis of suspected sepsis will include infants with suspicious clinical findings of infection, but no positive cultures or radiographs.
 - Pneumonia. The diagnosis of pneumonia will be confirmed by radiograph or positive blood culture.

13. Composite neonatal outcome comprised of fetal or neonatal death or RDS, Grade 3 or 4 IVH, PVL, Stage 2 or 3 NEC, BPD, Stage III or higher ROP, or early onset sepsis. Occurrence of any of the individual components is considered indicative of the outcome
14. Length of hospital stay, need for NICU or intermediate care admission and length of stay

5 Statistical Considerations

5.1 Data Relevant to the Primary Outcome

Hassan, who used a screening cervical length of between 10-20 mm, found a rate of preterm birth < 37 weeks of 26.7% in women treated with progesterone.¹² Because of the exclusion of women with cervical lengths between 0-9 mm it is highly plausible that the rate will be higher in the current trial. In an individual patient data meta-analysis of vaginal progesterone trials by Romero et al., the pooled preterm birth rate for singleton pregnancies was 34.7% for women with a short cervix of < 25 mm. However, Conde-Agudelo et al. in a systematic review and indirect comparison meta-analysis that contained overlapping but not exactly the same trials reported a rate of preterm birth < 37 weeks of 45.3%.³² Goya et al reported a 59% rate of spontaneous preterm delivery < 37 weeks for women with short cervix \leq 25 mm in the expectant management group.³³

5.2 Sample Size and Power

A one-third reduction in preterm birth < 37 weeks was selected as being clinically meaningful. If it is conservatively assumed that the rate of preterm birth < 37 weeks in the progesterone arm is between 28% and 35%, then a sample of 850 women is sufficient to detect a 33% reduction in preterm birth at 90% power. In addition this sample size yields more than 80% power to detect a 30% reduction, assuming a type 1 error of 5% 2-sided.

Table 2. Sample Size for Various Outcome Rates and Effect Sizes

PTB rate in Usual care arm (%)	Total sample size for 30% reduction	Total sample size for 33.3% reduction
Power=80% ($\alpha=0.05$; $\beta=0.2$)		
28	810	640
30	740	590
32	680	540
35	600	480
Power=90% ($\alpha=0.05$; $\beta=0.1$)		
28	1080	850
30	990	790
32	900	720
35	800	640

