5.4 Interim Analysis

The DSMC meets in person at least once per year and more often if recommended by the committee. Before each of the annual meetings, a formal detailed report will be written by the Biostatistical Coordinating Center (BCC) which presents all baseline variables, protocol adherence, side effects, all adverse events reported, as well as center performance in terms of recruitment, data quality, loss to follow-up and protocol violations.

Once sufficient patients have been accrued into the trial, the report will also include a formal interim analysis evaluating the primary outcome by treatment group. For this evaluation, a cohort of patients is chosen consisting of all patients randomized before a certain date so that the analysis cohort does not depend on gestational age at delivery.

The main statistical issue relevant to interim analysis is the problem of performing multiple tests of significance on accumulating data. For this trial, the group sequential method of Lan and DeMets will be used to characterize the rate at which the type I error is spent.³⁴ This method is flexible with regard to the timing of the interim analyses. It is expected that an interim analysis will be conducted at approximately 50% of the final sample size of 850.

Asymmetric stopping boundaries will be used for the Lan-DeMets procedure. The upper boundary which describes the stopping rule for benefit will be based on 1-sided type I error of .025 and the Lan-DeMets generalization of the O'Brien-Fleming boundary. The lower boundary will be based on a less stringent stopping rule: 1-sided type I error of .05 and the Lan-DeMets generalization of the Pocock type boundary.

It is often useful to calculate conditional power given the observed data to date, and conditional on the future data showing the originally assumed design effect. If this conditional power is low (under 10 percent) the DSMC may consider termination for futility if the accrual rate is slow with confidence that the Type II error is not greatly inflated.³⁵

It is recognized that any decision to terminate the study would not be reached solely on statistical grounds but on a number of complex clinical and statistical considerations.

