- Bacterial vaginosis/Nugent score at enrollment—Nugent \geq 7 with pH > 4.4
- Prior cervical surgery including LOOP/ LEEP

Loss to follow-up will be defined as no information regarding pregnancy prior to 37 weeks. Those defined as lost to follow-up will not be included in the primary analysis. It is expected that the loss to follow-up rate will be very low. For trials conducted by the MFMU Network, the loss to follow-up rate has typically been under 2 percent. However, a sensitivity analysis will be performed including patients lost to follow-up with different assumptions regarding their outcome, to determine whether the results are robust.

Since many of the secondary endpoints are dichotomous variables like the primary outcome, standard statistical methods for rates and proportions will be appropriate. The Wilcoxon rank sum test will be used to compare continuous variables, and survival analysis methodology may be used to compare time-to-event variables.

In general, analyses of data will be conducted to address the primary and secondary research questions of the trial, and other interrelationships among elements of study data of interest to the investigators and of relevance to the objectives of the study.

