Appendix A Design Summary

A Randomized Trial of Pessary in Singleton Pregnancies with a Short Cervix

OBJECTIVE: To determine whether pessary reduces the risk of preterm birth in women with a singleton gestation and a short cervix.

ORGANIZATION

Clinical Centers: Magee, UAB, Ohio State, Utah, Brown, Columbia, Case Western, UT-Houston, UNC, Northwestern, UTMB-Galveston, UPenn
 Subcommittee: [name] (Chair)

DESIGN

Major Eligibility Criteria: ❖ Singleton gestation
 ❖ Gestational age 16⁰ to 23⁶ wks
 ❖ Cervical length ≤ 20.0 mm

Groups: ❖ Usual Care (may include vaginal progesterone)
 ❖ Arabin Pessary + Usual Care

Random Allocation: Standard urn design; 1:1 allocation

Level of Masking: Unmasked

Stratification: ❖ Clinical site

Sample Size: ❖ 850

Assumptions: ❖ Outcome event=delivery < 37⁰ weeks gestation or fetal loss
 ❖ Usual care group event rate =28%
 ❖ Pessary group event rate =18.67% (33.3% reduction)
 ❖ Type I error = 2.5% (two sided with one comparison)
 ❖ Power =90%

Interim Analysis: ❖ Lan-DeMets group sequential method

SCHEDULED EVALUATIONS / DATA COLLECTION

Pre-Randomization: ❖ Cervical length measurement by trained sonographer
 ❖ Pregnancy, exposure and medical history

Randomization: ❖ Vaginal sample, vaginal Gram stain and vaginal pH

Post-randomization: ❖ Phone call to assess patient symptoms and compliance within 7 days of randomization
 ❖ Every four weeks: study visit to assess symptoms and compliance
 ❖ Study visit between 24 and 32wks: vaginal sample, vaginal Gram stain and vaginal pH
 ❖ Digital exam to ensure appropriate pessary placement (pessary group)

Delivery: ❖ Patient questionnaire 8 weeks after randomization and again at 37 wks gestation.
 ❖ Pessary group: assessed for fit or replacement, as needed
 ❖ Delivery and neonatal data

MANAGEMENT PROTOCOL

Both Groups: ❖ Vaginal progesterone per usual care and rescue cerclage if needed

Pessary Group: ❖ Placement management from randomization to < 37 wks

OUTCOME MEASURES

Primary: ❖ Delivery or fetal loss prior to 37 wks

Secondary: ❖ Randomization to delivery interval
 ❖ Gestational age at delivery
 ❖ Neonatal morbidity and mortality
 ❖ Lower genital tract or urinary tract infection
 ❖ Physician interventions including bedrest, cerclage, labor inhibition therapy

TIMETABLE

Enrollment: ❖ September 2016 to October 2019
 Data Collection: ❖ September 2016 to October 2019
 Closeout/Analysis: ❖ October 2019 to September 2021

References

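### At the 28% planning rate, 850 women give about 89% to 89.7% power for a one-third reduction, not the stated 90%; two Table 2 cells look 10 too low and no allowance for loss is stated

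*Combined protocol and SAP*

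**What the plan says.** Section 5.2 takes a one-third reduction as the target and a comparator rate of 28% to 35%, and concludes "then a sample of 850 women is sufficient to detect a 33% reduction in preterm birth at 90% power", "assuming a type 1 error of 5% 2-sided". Table 2 prints 850 for 28% with a 33.3% reduction at 90% power, and 640 for the same pair at 80% power. Appendix A lists "Usual care group event rate =28"%, "Pessary group event rate =18.67% (33.3% reduction"), 90% power, 850 women and "Standard urn design; 1:1 allocation". It gives the error rate as "Type I error = 2.5% (two sided with one comparison").

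Two later provisions bear on how many women are analysed and at what critical value. Section 5.5 says "Those defined as lost to follow-up will not be included in the primary analysis" and puts the usual network loss below 2 percent. Section 5.4 says "It is expected that an interim analysis will be conducted at approximately 50% of the final sample size of 850", with an O'Brien-Fleming-type benefit boundary at one-sided .025. Section 5.2, Table 2 and Appendix A state no allowance for either, and section 5.2 names neither a sample size formula nor a rounding rule.

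**The concern.** The cell that sets the size of the trial is one of only two in Table 2 that break the pattern of the other 14. In addition, 850 is the number randomized, while the primary analysis uses a slightly smaller number. Both effects lower power, and both bite at 28%, which is the rate in Appendix A and the lower end of the range for which section 5.2 claims 90%. What is at stake is the accuracy of the stated power, including the baseline that the monitoring committee will have when it reviews the usual-care rate under section 5.3.

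**Working it through.** **Inputs.** Usual-care rate p1 = 0.28 and pessary rate p2 = 0.28 × 2/3 = 0.18667 (Appendix A); 1:1 allocation (Appendix A); 5% two-sided (section 5.2); a simple comparison of two proportions (section 5.5); loss under 2% (section 5.5), taken here as 0%, 1% and 2%; one look at 50% with O'Brien-Fleming-type spending (section 5.4).

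**Step 1: reproduce Table 2.** The pooled-variance formula for the total is

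N = 2 × [1.96 √(2p̄q̄) + z_β √(p1q1 + p2q2)]² / (p1 − p2)²,

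rounded up to the next ten. Each entry is the formula value, then the printed value.

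| Usual-care rate | 80%, 30% red. | 80%, 33.3% red. | 90%, 30% red. | 90%, 33.3% red. |
|---|---|---|---|---|
| 28% | 804.6 / 810 | **642.4 / 640** | 1076.1 / 1080 | **858.9 / 850** |
| 30% | 734.0 / 740 | 586.3 / 590 | 981.6 / 990 | 783.9 / 790 |
| 32% | 672.2 / 680 | 537.2 / 540 | 898.9 / 900 | 718.2 / 720 |
| 35% | 592.8 / 600 | 474.2 / 480 | 792.6 / 800 | 633.8 / 640 |

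Fourteen cells match. The two in bold would round up to 650 and 860.

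For the design cell: p̄ = 0.23333, √(2p̄q̄) = 0.59815, √(p1q1 + p2q2) = 0.59449 and p1 − p2 = 0.09333. Then [1.96 × 0.59815 + 1.2816 × 0.59449]² / 0.0087111 = 429.5 per arm, or 858.9 in total.

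**Step 2: try other standard formulas for the design cell.** Unpooled variance gives 852.6 (853 women) and arcsine 855.3 (856). Both exceed 850, if only slightly. Rounded up to the next ten, arcsine matches 13 of the 16 cells, including the 640, and unpooled matches 5.

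**Step 3: power at 850, all analysed, no look.** With n = 425 per arm:

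Power = Φ{[0.09333 × √425 − 1.96 × 0.59815] / 0.59449} = Φ(1.2645) = 89.7%.

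**Step 4: loss and the look.** The O'Brien-Fleming-type boundary at half the information is z = 2.963, then 1.969 at the end. Power is one minus the bivariate normal probability of crossing neither, with correlation √0.5. A loss of 1% leaves 841.5 women and 2% leaves 850 × 0.98 = 833.

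| Analysed | No look | With look |
|---|---|---|
| 850 (no loss) | 89.7% | 89.6% |
| 841.5 (1% lost) | 89.4% | 89.3% |
| 833 (2% lost) | 89.1% | 89.0% |

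The look costs about 0.1 point, and the Pocock-type lower boundary nothing measurable under the design effect. The discretionary futility rule is not counted.

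**Step 5: the rest of the claimed range, one-third reduction.**

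| Usual-care rate | 850, no look | 833, with look |
|---|---|---|
| 29% | 91.0% | 90.3% |
| 30% | 92.2% | 91.6% |
| 32% | 94.2% | 93.7% |
| 35% | 96.4% | 96.0% |

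With all 850 analysed and no look, 90% is reached from about 28.3%. With 2% lost and the look, it is reached from just above 28.7%.

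**Step 6: the second claim in section 5.2** (more than 80% power for a 30% reduction). At 28% power is 82.1% with all 850 and no look, and 81.2% with 833 and the look. The claim holds.

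**Step 7: the error rate in Appendix A.** Read literally as 2.5% two-sided, the same formula needs 1,016 women for 90% power, and 850 gives 83.7%.

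**The case against.** The strongest reply is that nothing of substance is wrong. Power is stated as a whole percent, and 89.7% rounds to 90%. The printed 850 is within 1.2% of the best-fitting formula, and that formula is a reconstruction. Loss of 2% is an upper value, and section 5.5 expects loss to be very low and adds a sensitivity analysis that includes the women lost. The 28% is deliberately conservative: section 5.1 argues that a rate above its 26.7% source figure is highly plausible and cites 34.7%, 45.3% and 59%. Section 5.3 also lets the monitoring committee recommend a new sample size after 150 deliveries.

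Most of this stands, and it limits the point to a correction of wording. It does not remove it. None of the three formulas tried brings the design cell down to 850, and the exclusion of women lost to follow-up is written into the plan without an allowance. The sensitivity analysis does not restore the power of the primary analysis.

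A reader might also infer that the two cells came from cutting the pessary rate to 18.6%, which gives 632.6 and 845.9, hence 640 and 850. That is conjecture. The documents never mention 18.6%, and the same truncation at 35% (to 23.3%) gives 629.9, hence 630, where Table 2 prints 640.

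**Conclusion.** The stated 90% is slightly too high at the planning rate: 89.7% with everyone analysed, and 89.0% to 89.4% with 1% to 2% lost. The shortfall is at most about 1 point and ends by a usual-care rate of about 29%. It rests on 5% two-sided, loss no greater than 2%, one look at 50%, and the usual normal approximation. That the two cells are 10 too low holds relative to the inferred formula.

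Two stronger readings are tempting and not supported. One is that the trial is underpowered and needs more women. Holding 90% at exactly 28% with 2% loss and the look would take 862 analysed, or 862 / 0.98 ≈ 880 randomized, but the gain is 1 point at a deliberately low rate that section 5.3 already monitors. The other is that the trial really runs at 2.5% two-sided with 83.7% power. Section 5.2, Table 2 and the one-sided .025 benefit boundary in section 5.4 all correspond to 5% two-sided, so the Appendix A line is an inconsistency to reconcile and not evidence of a different design.

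**What to change.** - Keep 850.
- In Table 2, change 640 to 650 and 850 to 860 for 28% with a 33.3% reduction, or state the formula and rounding that produce the printed values.
- In section 5.2 and Appendix A, say that 850 randomized women give about 89% power at a 28% usual-care rate for a one-third reduction, and at least 90% from about 29% to 35%, allowing for up to 2% lost to follow-up and one interim look. The statement on a 30% reduction can stay.
- In the same edit, reconcile the type I error line in Appendix A with section 5.2, because the restated power assumes 5% two-sided.

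The cost is a few lines of text, two table cells and a slightly less favourable power figure. No extra women are needed and the analysis does not change.
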